3.1.4.5 Analysis of covariance (ANCOVA) analysis for Efficacy Analysis with Continuous Variables

In addition, treatment comparisons for continuous efficacy variables will also be assessed using an ANCOVA model.

The ANCOVA model includes treatment groups and baseline values. For each treatment comparison performed, the LSM for each treatment group, an estimate of the difference between treatments, corresponding 95% CI and p-value will be presented. Type III sums of squares for the LSM will be used for the statistical comparison. Below is the SAS code for the ANCOVA model.

```
Proc mixed DATA=XX;
Class TRT;
Model AVAL = TRT BASE;
lsmeans TRT / cl alpha=0.05 pdiff;
Run;
```

3.1.5 Study Day

The study day for all assessments prior to the first study drug administration is calculated as the difference between the date of the event or measurement (e.g., adverse event [AE] onset date, assessment date, sample collection date, etc.) and the start date of study treatment. The day before the start of study treatment is Study Day -1.

The study day for all post assessments after the first study drug administration is calculated as the difference between the date of the event or measurement (e.g., AE onset date, assessment date, sample collection date, etc.) and the start date of study treatment plus one day. The first day of study treatment is Study Day 1.

3.1.6 Baseline

Baseline value is defined as the valid and last non-missing value obtained within 29 days prior to subject receiving the first study medication, unless otherwise stated under the related assessment section. Baseline can be the day before the first study medication or on the same day as the first study medication if a pre-dose assessment is available. Subjects without data on a parameter before the first study medication will have a missing baseline for this parameter.

For patients who randomized in placebo group in double blinded period and re-randomized in open label period, the baseline value of open label period is defined as the valid and last non-missing value obtained prior to subject receiving the first dose of belumosudil.

3.1.7 Handling of Incomplete or Missing Data

The imputed methods for missing data are described as below for the following situations.

3.1.7.1 Imputation for CRISS Score

Linearization and last observation carried forward (LOCF) method will be used when calculating the primary endpoint CRISS if any of the component scores is missing.

The linearization method will be used when there is a missing observation followed by a non missing observation. The missing value will then be imputed as the average of the previous non missing observation and the next non missing observation. If there is no next non missing observation in the current treatment group then just the last observation will be used.

For patients discontinuing investigational product for any reason, the last non-missing observation before discontinuation will be carried forward to the corresponding endpoint for evaluation. For patients randomized to belumosudil at Week 1, the last non-missing observation in double-blind treatment period will be carried forward to open-label treatment period. For patients randomized to placebo at Week 1, LOCF imputation will be performed within treatment period. The last non-missing observation in double-blind treatment period will not be carried forward to open-label treatment period.

Randomized patients without at least 1 postbaseline observation will not be included for evaluation.

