- To evaluate the efficacy of belumosudil compared to placebo at Week 24 for:
 - Modified Rodnan Skin Score (mRSS)
 - Forced Vital Capacity (FVC)
 - o Physician global assessment
 - o Patient global assessment
 - Scleroderma Health Assessment Questionnaire— Disability Index (SHAQ-DI)

Kadmon Corporation, LLC

Page 6 of 99

27 May 2021

	To evaluate the efficacy of belumosudil at Week 52 compared to baseline for subjects randomized to belumosudil for the parameters in the bullet above
	 To assess changes in lung fibrosis, via high resolution computerized tomography (HRCT), performed at baseline, Weeks 24 and Week 52 only in subjects with ILD at screening
	 To assess pharmacokinetics (PK) of belumosudil by sparse sampling of belumosudil on Weeks 4 and 8 (i.e., Days 29 and 57) immediately prior to belumosudil dosing and 3 hours post- dose
	 To assess the safety of belumosudil compared to placebo in subjects with dcSSc by examining the percentage of subjects with treatment-emergent adverse events (CTCAE v5.0) in subjects with diffuse cutaneous systemic sclerosis
	Exploratory Objectives
	 To evaluate changes in biomarkers of endothelial cell dysfunction, fibrosis, immune system function, and cytokine alterations from subjects receiving belumosudil or placebo
	 To assess histology and gene expression from skin biopsies taken from subjects at baseline, Week 24, and optionally at Week 52
Study Design	Phase 2, double-blind, placebo-controlled, randomized, multicenter trial in subjects with dcSSc with open-label extension.
Methodology	Subjects who have signed an IRB/IEC-approved informed consent form and met all of the inclusion/exclusion criteria will be enrolled. A total of 60 subjects will be randomized into 3 groups (1:1:1) to receive orally administered belumosudil 200 mg once daily (QD; n = 20), belumosudil 200 mg twice daily (BID; n = 20), or matched placebo (n = 20) for 28 weeks. The study will be double-blinded for the first 28 weeks followed by an open-label extension of 24 weeks. After unblinding, the subjects in Group 1 and 2 will continue on the same belumosudil dose whereas the subjects in the placebo group will be re-randomized to one of the belumosudil doses (200 mg QD or 200 mg BID) in 1:1 fashion.
	The primary endpoint will be analyzed using Week 24 data.

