Pregnancy Test ^k	X	X	X	X	X	X	X	X	X	X	X	X	X	X	X	X	X	X
Study diary (dispense/collect)		х		х	х	Х	Х	Х	Х	Х	х	х	Х	х	Х	х		х
Study drug administration ¹		х	X	x	x	x	x	х	Х	Х	х	х	Х	х	Х			х
Dispense/Collect study drug ¹		х		х	х	х	х	х	X	X	х	х	X	х	X	x		х
Concomitant																		

Abbreviations: CRISS = Combined Response Index in Diffuse Cutaneous Systemic Sclerosis; ECG = electrocardiogram; EDC = electronic data capture; EOT = End-of-Treatment; FVC = forced vital capacity; HRCT = high-resolution computerized tomography; ICF = informed consent form; ILD = interstitial lung disease; mRSS = modified Rodnan Skin Score; PE = physical examination; PFT = pulmonary function test; SHAQ—DI = Scleroderma Health Assessment Questionnaire—Disability Index

The ICF must be signed before any study procedure begins.

Medications

Adverse Events

Kadmon Corporation, LLC

Page 86 of 99

27 May 2021

To be collected from the date that the ICF is signed until 28 days after last dose of Belumosudil.

[figure not shown]
- b. Re-randomization of the placebo group to one of two arms will take place after the un-blinding procedures take place.
- c. CRISS will not be performed on site, but rather will be calculated outside of EDC.
- d. mRSS, SHAQ-DI, FVC, physician global assessment and patient global assessment will be performed at baseline Day 1, Day 57, Day 113, Day 169, Day 197, and then every 8 weeks thereafter until Week 52. In addition, after their last dose of study drug (4-Week Follow-Up Visit). mRSS and FVC will also be performed at screening as one of the inclusion criteria. FVCs should be performed if PFT is not performed at the same visit.
- e. HRCT and PFTs, to include FEV₁, FVC, DL_{CO} (corrected for Hb), TLC, and RV, will be performed at baseline, Day 169, and Day 365 (each ± 7 days). In addition, PFTs will be performed after their last dose of study drug (4-Week Follow-Up Visit). If the HRCT or PFTs is performed within one month of the EOT visit, it does not need to be done again at the EOT visit.
- f. HRCT will be done only in subjects at Day 1, Day 169, and Day 365 (each ± 7 days) if they have confirmed ILD at baseline. This is not required at the End of Treatment visit.
- g. Double punch Skin biopsies are MANDATORY for all subjects on Day 1 and Day 169 and Optional on Day 365 and will be obtained from the dorsal mid-forearm for Gene Profiling. This assessment is not required for End of Treatment.

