3 STATISTICAL METHODS

3.1 General Methods

3.1.1 Analysis Periods

The analysis will be split into three separate periods.

- The Double-Blinded Period analysis will be the period from week 0 to week 24.
- The Double-Blinded Period (0 week 28) will be the period from week 0 to week 28.
- The Combined Double-Blinded Period and Open-Label Period will be the period from week 0 to week 52.

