3.8 Definition of Efficacy Endpoints

3.8.1 Primary Efficacy Endpoint: CRISS

The primary efficacy endpoint is Combined Response Index in Diffuse Cutaneous Systemic Sclerosis (CRISS).

CRISS is a 2-step process for use in a clinical trial.

Step 1: patients who develop new onset of renal crisis, new onset or worsening of lung fibrosis, new onset of pulmonary arterial hypertension, new onset of left ventricular failure during the trial are considered as not improved and assigned a probability of improving equal to 0.0.

Step 2: For the remaining patients, step 2 involves computing the predicted probability of

improving for each individual, using the equation shown below.

$$\frac{\exp\left[-5.54 - 0.81 * \Delta_{MRSS} + 0.21 * \Delta_{FVC\%} - 0.40 * \Delta_{Pt-glob} - 0.44 * \Delta_{MD-glob} - 3.41 * \Delta_{HAQ-DI}\right]}{1 + \exp\left[-5.54 - 0.81 * \Delta_{MRSS} + 0.21 * \Delta_{FVC\%} - 0.40 * \Delta_{Pt-glob} - 0.44 * \Delta_{MD-glob} - 3.41 * \Delta_{HAQ-DI}\right]}$$

where Δ_{MRSS} indicates the change in mRSS from baseline to follow up, $\Delta_{FVC\%}$ denotes the change in FVC% predicted from baseline to follow up, $\Delta_{Pt-glob}$ indicates the change in patient global assessment, $\Delta_{MD-glob}$ denotes the change in physician global assessment, and Δ_{HAQ-DI} is the change in HAQ-DI. All changes are absolute change (Time₂-Time_{baseline}).

As patient global assessment and physician global assessment are based on a VAS of 0 (Extremely Poor)-100 (Excellent) in CRF. When calculating the CRISS score, these 2 scores should be divided by 10 firstly to make it in a 0-10 scale. If any of the component scores are missing, CRISS score will be calculated based on the imputed component score using LOCF method.

The outcome is a continuous variable between 0.0 and 1.0 (0-100%). A higher score indicates greater probability of improvement. A CRISS score ≥ 20% is considered as the minimal detectable difference and will be described as CRISS20 in the SAP. A CRISS score >= 60% is considered as the minimally important difference and will be described as CRISS60 in the SAP. This will be the primary variable for efficacy.

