Analyses of the primary efficacy endpoints will be conducted using the mITT population. The number and percentage of patients achieving CRISS60 response will be summarized by treatment group. Treatment comparisons between each belumosudil dose regimen and placebo in the proportion of patients achieving an CRISS60 response will be analyzed using a logistic regression analysis with treatment in the model.

The continuous CRISS score will be summarized as a continuous endpoint at all post baseline scheduled assessment visits. The continuous CRISS score will be analyzed using the MMRM model, and a t-test comparison. If the data is not normally distributed then the Wilcoxon-Mann-Whitney model will be used instead of a t-test. Missing data will be imputed using the Linearization method The linearization method will take the average of the last observation and the next non missing observation. If there is no next non missing observation in the current treatment group then just the last observation will be used.

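### The SAP gives two different rules for a missing CRISS component, does not say which governs, and names no latest visit whose value may fill a Week 24 gap

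*SAP*

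**What the plan says.** Three places in the SAP deal with a missing CRISS component or score.

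- **SAP 3.8.1, definition of the endpoint:** "If any of the component scores are missing, CRISS score will be calculated based on the imputed component score using LOCF method". Averaging is not mentioned.
- **SAP 3.1.7.1, the imputation section:** it names both linearization and LOCF. Where a missing value is followed by an observed one, "The missing value will then be imputed as the average of the previous non missing observation and the next non missing observation". If the current treatment group holds no later value, the last one is used alone. For subjects who stop study drug, "the last non-missing observation before discontinuation will be carried forward to the corresponding endpoint for evaluation". On crossing from the blinded to the open-label period: "For patients randomized to belumosudil at Week 1, the last non-missing observation in double-blind treatment period will be carried forward to open-label treatment period". For subjects randomized to placebo, LOCF stays within each treatment period.
- **SAP 3.8.1, paragraph on the continuous score:** "The linearization method will take the average of the last observation and the next non missing observation", with the same fallback. It does not say whether component values or CRISS scores are averaged.

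On timing, Protocol Appendix A, footnote d, schedules the components at baseline and then at "Day 57, Day 113, Day 169, Day 197, and then every 8 weeks thereafter until Week 52". The Protocol Synopsis says "The primary endpoint will be analyzed using Week 24 data". SAP 3.1.1 says "The Double-Blinded Period analysis will be the period from week 0 to week 24", and it also defines a second double-blind period that runs to Week 28. Under Protocol 4.3 each subject is unblinded on reaching 28 weeks, and Appendix A, footnote o, places this at the Week 28 visit.

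**The concern.** A missing component is the one situation in which the Week 24 CRISS depends on an imputation rule, and the SAP gives two. The component visits on either side of Week 24 (Day 169) are Week 16 (Day 113) and Week 28 (Day 197). LOCF therefore fills a Week 24 gap from Week 16 alone, while averaging brings in Week 28. CRISS60 is a threshold on a steep logistic function, so a modest difference in one imputed component can change responder status.

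The placing of the two statements makes things worse. LOCF appears where the endpoint is defined, and averaging appears in the paragraph on the continuous score. An analyst could in good faith use LOCF for CRISS60 and averaging for the continuous score, so that the two analyses of the same endpoint rest on different data for the same subject.

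The second gap is the cut-off. The later value is limited only by the words current treatment group, with no visit named. Week 28 is also the unblinding visit, and the Protocol does not say whether the mRSS and global assessments are completed before the subject's treatment is revealed. Protocol 5.2.9 lists re-randomization ahead of them, although list order need not be visit order.

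**Working it through.** The plan states no figure on this point, so there is nothing to reproduce. The check compares the rules and then runs the SAP's own CRISS equation under each.

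**1. The rules for a Week 24 gap with Week 16 and Week 28 observed**

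| Source | Imputed component |
|---|---|
| SAP 3.8.1, endpoint definition | Week 16 value |
| SAP 3.1.7.1 | (Week 16 + Week 28) / 2 |
| SAP 3.8.1, continuous score | Average, of components or of scores not stated |

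**2. Equation (SAP 3.8.1)**

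CRISS = exp(x) / (1 + exp(x)), with x = −5.54 − 0.81·ΔmRSS + 0.21·ΔFVC% − 0.40·ΔPatient global − 0.44·ΔPhysician global − 3.41·ΔHAQ-DI.

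Assumed for illustration: ΔFVC% = +2, ΔHAQ-DI = −0.25, both globals 0, and only mRSS missing at Week 24. Then x = −5.54 + 0.42 + 0.8525 − 0.81·ΔmRSS = −4.2675 − 0.81·ΔmRSS. CRISS reaches 0.60 when x = ln(0.6/0.4) = 0.4055, that is, at ΔmRSS = −(4.2675 + 0.4055)/0.81 = −5.77.

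**3. Results**

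- *mRSS change −3 at Week 16, −9 at Week 28.* LOCF: x = −1.8375, CRISS 0.137. Averaging: (−3 − 9)/2 = −6, x = 0.5925, CRISS 0.644. Averaging creates a CRISS60 response.
- *mRSS change −6 at Week 16, −5 at Week 28.* LOCF: 0.644. Averaging: (−6 − 5)/2 = −5.5, x = 0.1875, CRISS 0.547. Averaging removes a response.
- *First case again, averaging scores instead of components.* The score at −9 is 0.954 (x = 3.0225), and (0.137 + 0.954)/2 is about 0.545. This is below 0.60, whereas averaging the component gives 0.644.
- *All other changes set to 0.* The 0.60 threshold moves to −7.34. Week 16 at −6 then −10: LOCF 0.336, averaging 0.719. Week 16 at −8 then −4: 0.719 and 0.336. Week 16 at −4 then −6: 0.091 and 0.184, with no change of status.

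**4. Size in an arm**

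One reclassified subject is 1/20 = 5 percentage points. If 1 to 3 of 20 were affected (assumed) and all flipped the same way, the shift would be 5 to 15 points. The documents give no rate of missing Week 24 components.

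**5. The cut-off**

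Suppose Week 28 is missing too. The next scheduled components are at Week 36. A belumosudil subject is still on the same regimen (KQD/KQD or KBID/KBID in SAP 2.4), so Week 36 can be read as within the current treatment group. A placebo subject has been switched, so it cannot. SAP 2.4 also defines KQD, KBID and PBO as groups for the first 28 weeks only. On those definitions every arm stops at Week 28.

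**The case against.** Several points on the other side stand.

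- **SAP 3.1.7.1 is ordered internally.** A reader might infer that the SAP gives no order of precedence at all. That goes too far. The section averages first and falls back on the last value, and it has a specific carry-forward rule for subjects who stop study drug. On an ordinary reading the specific rule displaces the general one, so a 28-day follow-up value would not be averaged in. What stays open is whether an end-of-treatment (EOT) value counts as before discontinuation.
- **Open-label values are not plainly allowed.** A reader might infer that the plan feeds them into the belumosudil arms only. The documents do not establish this. SAP 2.4 supports a 28-week limit, both Week 24 and Week 28 would have to be missing, and the sentence carrying belumosudil values across periods works forward in time, not backward.
- **Using Week 28 is not wrong in itself.** A reader might infer from the Synopsis and the Week 0 to 24 analysis period that later values are barred. Those statements identify the endpoint visit and a period; they do not address imputation. Interpolation uses a later value by design, Week 28 is the scheduled end of double-blind treatment in every arm, and it lies 28 days from Day 169 against 56 days for Week 16. LOCF is not shown to be better.
- **The numerical cases were chosen to cross the threshold**, and one shown above does not. The trial is exploratory and not powered for a test.

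None of this reconciles SAP 3.8.1 with 3.1.7.1. Reading LOCF in the endpoint definition as shorthand for the fuller rule is possible, but the text does not say so.

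**Conclusion.** The point holds in this form: the SAP states LOCF alone in one place and averaging first in another for the same missing component, does not say which governs, leaves open whether the continuous-score paragraph averages components or scores, and names no latest eligible visit. The choice can reverse a subject's CRISS60 status in either direction, at 5 percentage points per subject with 20 per arm. The individual scores rest on assumed component changes. The effect on the treatment comparison cannot be computed, because the amount of missing Week 24 data is not given.

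A reader might also infer that the rule would be picked with treatment arms known. The documents do not say when it would be fixed. They show only that subjects are unblinded one by one at Week 28, so an unsettled rule leaves that possibility open. That is reason enough to settle it, even in an exploratory trial, since the SAP plans odds ratios, confidence intervals and p-values, and Protocol 9.7.1 says the results are to guide follow-up studies.

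**What to change.** In SAP 3.1.7.1:

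- State one rule at component level. Have both parts of 3.8.1 refer to it, and apply it to CRISS60 and to the continuous score.
- State that no value after the Week 28 end-of-double-blind visit, and no Week 28 value collected after that subject is unblinded, may fill a Week 24 gap in any arm.
- Confirm that carry-forward after stopping study drug overrides averaging, and say whether an EOT value counts as before discontinuation.

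Whether the rule uses Week 28 (averaging) or does not (LOCF) is the sponsor's choice. It should be fixed before any unblinded data are reviewed, with the other rule run as a sensitivity analysis.

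The cost is SAP wording and one additional analysis. No change to visits or data collection is needed.

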1. INTRODUCTION

1.1 BACKGROUND

Systemic sclerosis, also known as scleroderma, is a chronic autoimmune disease primarily affecting the skin, but with systemic manifestations. Diffuse cutaneous systemic sclerosis is a more serious form of the disease and is often rapidly progressive, involving not only the skin but also internal organs including kidney, heart, and lungs.⁽¹⁾

The estimated annual incidence of systemic sclerosis in the United States is 20 cases per million with a prevalence of 240 cases per million population. (2,3,4) Racial disparities exist and there is an increased incidence and severity in African-Americans. Women are far more likely to acquire the disease and make up 80%–90% of the systemic sclerosis population. (5)

It has been estimated that up to 60% of systemic sclerosis patients will develop interstitial lung disease. This interstitial disease begins with an inflammatory alveolitis suggesting that anti-inflammatory therapy may be of benefit at early stages. (6,7)

Systemic sclerosis has the highest case-specific mortality among all systemic autoimmune diseases. Pulmonary hypertension, pulmonary fibrosis, and cardiac complications are the most frequent causes of death. The single most common cause of mortality is pulmonary fibrosis from interstitial lung disease.⁽⁸⁾

There remains substantial unmet need for therapies with improved tolerability and effectiveness for patients with deSSc.

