3.9 TREATMENT DISCONTINUATION

Treatment discontinuation reasons include the following:

- An AE requiring permanent discontinuation of study drug
- Investigator decision
- Clinically significant disease progression. For example:
 - o mRSS increase ≥ 5 units
 - Absolute decrease in FVC (% predicted) ≥10% or absolute decrease in diffuse capacity of the lungs for carbon monoxide (DLco) (corrected for Hb) of > 15%
 - o Renal crisis
- Study stopping rules for the sponsor (Section 9.6.1)
- Subjects meeting criteria for discontinuation from the study (Section 9.6.2)

- Voluntary withdrawal by subject
- Noncompliance to protocol
- Subject lost to follow-up
- Termination of the study by sponsor
- Subject death

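### A death before Week 24 without a CRISS Step 1 event is handled by carry-forward, so a subject who has died can count as a CRISS60 responder

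*SAP*

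**What the plan says.** SAP 3.8.1 scores CRISS in two steps. Step 1 gives zero to "patients who develop new onset of renal crisis, new onset or worsening of lung fibrosis, new onset of pulmonary arterial hypertension", and the list closes with "new onset of left ventricular failure during the trial are considered as not improved and assigned a probability of improving equal to 0.0". Everyone else goes to the equation: "For the remaining patients, step 2 involves computing the predicted probability of" improving.

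Missing data are covered twice. SAP 3.1.7.1 states: "For patients discontinuing investigational product for any reason, the last non-missing observation before discontinuation will be carried forward to the corresponding endpoint for evaluation". SAP 3.8.1 adds: "If there is no next non missing observation in the current treatment group then just the last observation will be used". SAP 3.1.7.1 ends with an exclusion: "Randomized patients without at least 1 postbaseline observation will not be included for evaluation".

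Protocol 3.9 includes "Subject death" in its list of treatment discontinuation reasons. In the SAP, deaths appear only in the safety listings (3.9.1). No efficacy rule in either document mentions them.

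**The concern.** Read together, these rules treat death like any other dropout. A subject who improves by Week 16 and dies before Week 24 of a cause outside the Step 1 list is carried to Week 24 as improved. A living subject with one of the four organ events gets the lowest possible score, so the worst outcome can rank above a lesser one in both the CRISS60 analysis and the continuous score. The error favours whichever arm has more deaths after an early response.

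The scenario is relevant to the disease. Protocol 1.1 says: "Systemic sclerosis has the highest case-specific mortality among all systemic autoimmune diseases". The study is also meant to guide follow-up studies (Protocol 9.7.1), so a scoring rule set here may be reused.

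**Working it through.** There is no plan figure to reproduce. The check is a reading of the rules, then an evaluation of the SAP's own equation.

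**1. Is death a Step 1 event?** No. The list in SAP 3.8.1 has four entries: renal crisis, new or worsening lung fibrosis, pulmonary arterial hypertension and left ventricular failure. A subject who dies without one of these is among the remaining patients and goes to Step 2.

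**2. Does carry-forward apply?** Yes, by two routes. Protocol 3.9 makes death a discontinuation reason, and SAP 3.1.7.1 covers discontinuation for any reason. If someone argues that dying is not discontinuing the product, the fallback in SAP 3.8.1 gives the same result, because no later observation exists.

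**3. Is there a score to carry?** Yes. CRISS components are collected at Day 57 (Week 8) and Day 113 (Week 16) before the Day 169 (Week 24) assessment (Protocol Appendix A).

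**4. Can that score be a responder score?** From SAP 3.8.1, CRISS = exp(x)/(1 + exp(x)), with

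x = -5.54 - 0.81·ΔmRSS + 0.21·ΔFVC% - 0.40·ΔPatient - 0.44·ΔPhysician - 3.41·ΔHAQ-DI.

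Both global assessments are held at no change.

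| Change from baseline | x | CRISS | CRISS60? |
|---|---|---|---|
| mRSS -5 only | -5.54 + 4.05 = -1.49 | 0.184 | no |
| mRSS -6 only | -5.54 + 4.86 = -0.68 | 0.336 | no |
| mRSS -7 only | -5.54 + 5.67 = 0.13 | 0.533 | no |
| mRSS -8 only | -5.54 + 6.48 = 0.94 | 0.719 | yes |
| mRSS -6, FVC% +3, HAQ-DI -0.25 | -5.54 + 4.86 + 0.63 + 0.8525 = 0.8025 | 0.691 | yes |

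At the 20% threshold that Protocol 6.1 calls clinically meaningful, mRSS -6 alone is enough.

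**5. Effect of one such death**, compared with scoring it 0.0, in an arm of 20 (SAP 3.1.3):
- CRISS60 rate: 1/20 = 5 percentage points. Two deaths: 2/20 = 10 points.
- Mean CRISS at a carried score of 0.719: 0.719/20 = 0.036. If CRISS is not normal, the SAP switches to ranks and Wilcoxon-Mann-Whitney, so this mean shift is not what would be tested.
- A death whose carried score is below 0.60 does not change the CRISS60 count.

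**6. Deaths before the first post-baseline assessment.** These subjects have nothing to carry and are excluded by the last sentence of SAP 3.1.7.1, although the mITT population includes everyone dosed. With an assumed 8 responders, one such death gives 8/19 = 42.1% instead of 8/20 = 40.0%. Neither early nor later deaths count as failures unless a Step 1 event was recorded.

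**7. Week 52.** SAP 3.1.7.1 carries double-blind values into the open-label period for subjects randomized to belumosudil but not for placebo. A belumosudil subject who dies at Week 20 therefore also keeps a score at Week 52, while a placebo subject who dies then does not.

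**The case against.** The strongest reply is that the case will be rare. Protocol 1.1 names pulmonary hypertension, pulmonary fibrosis and cardiac complications as the most frequent causes of death, with fibrosis the single most common. Step 1 covers much of that ground, so many disease-related deaths would already score 0.0. Entry criteria also remove subjects with NYHA class II-IV heart failure, low FVC or recent renal crisis (Protocol 3.5). This stands: it limits how often the rule misfires, but not what the rule does when it applies.

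A reader might infer that such a case is likely. Assuming 24-week mortality m of 1-3%, 1 - (1 - m)^60 gives 45-84%. The documents do not support that reading. They give no mortality rate for this population, and the figure is the chance of any death. A misclassified responder also needs the death to fall after the first efficacy visit, no Step 1 event, and a last score of at least 0.60. As an illustration only, assume 16/24 of deaths fall after Week 8, 30-50% of those lack a Step 1 event, and 30-50% of those were at CRISS60. The expected number is then 60 × 0.01 × 16/24 × 0.3 × 0.3 = 0.04 to 60 × 0.03 × 16/24 × 0.5 × 0.5 = 0.30. The chance of at least one is roughly 4-26%.

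A reader might also infer that one death could reverse the trial's conclusion. Sample size and power are not driven by hypothesis testing (Protocol 9.7.2, SAP 3.1.3) and no success rule is stated, so there is no declared threshold to cross. Deaths are listed individually, so a responder who had died could be found in a 60-subject report. Both points lower the severity. Neither justifies the score.

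**Conclusion.** Wrong as written. Applying the SAP exactly, a subject who dies between the Week 8 or Week 16 assessment and Week 24 without a Step 1 event keeps the last score and can be counted as a CRISS60 responder, above a survivor with new pulmonary arterial hypertension at 0.0. Each such death with a carried score of at least 0.60 moves a 20-subject arm by 5 points. That size is arithmetic from the planned arm size. The number of such deaths is unknown and probably small. The point should be fixed, but for an exploratory study it is not a condition for proceeding.

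**What to change.** Three changes to the SAP:

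1. In 3.8.1, add to Step 1: *death from any cause recorded before the Week 24 assessment (before Week 52 for the Week 52 score)*. Score it 0.0 and CRISS60 non-responder at every scheduled visit after death. Scores observed before death stay at their own visits.
2. In 3.1.7.1, add: *No value is carried forward past the date of death.*
3. In 3.1.7.1, exempt deaths from the exclusion of subjects without a post-baseline observation, so that early deaths in the mITT population also score 0.0. Without this, the new Step 1 text and the exclusion would conflict.

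The cost is a few sentences and a small programming change, with no new data collection if the rule is limited to recorded deaths. That limit must be stated. Safety data run to 28 days after the last dose (Protocol 9.1), later deaths are reportable only if believed drug-related (Protocol 9.3.6), and early discontinuers have no scheduled contact after the 28-day visit. An unrelated death at Week 20 in a subject who stopped at Week 9 might not be recorded. The wording should be settled before CRISS results by arm are examined, so that the choice cannot appear to depend on them.
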